6.7.2 Instruction for prescribing and taking study treatment

A description of eltrombopag, dose and frequency is provided in [Table 6-2](#).

- Patients should take eltrombopag at approximately the same time each day either 1 hour before eating or 2 hours after eating.
- For 2 hours before taking eltrombopag and 4 hours after taking eltrombopag, patients should **avoid eating** dairy products, and calcium- and magnesium-rich foods
- Patients should be instructed not to make up missed doses. Patients who miss a dose of eltrombopag should wait and take the next scheduled dose. Patients should not take more than one dose of eltrombopag in one day.

7 Informed consent procedures

Eligible patients may only be included in the study after providing (witnessed, where required by law or regulation), Institutional Review Board (IRB)/Independent Ethics Committee (IEC)-approved informed consent.

If applicable, in cases where the patient's representative(s) gives consent (if allowed according to local requirements), the patient must be informed about the study to the extent possible given his/her understanding. If the patient is capable of doing so, he/she must indicate agreement by personally signing and dating the written informed consent document.

Informed consent must be obtained before conducting any study-specific procedures (e.g. all of the procedures described in the protocol). The process of obtaining informed consent must be documented in the patient source documents.

Novartis will provide to investigators in a separate document a proposed informed consent form that complies with the International Council of Harmonisation (ICH) Good Clinical Practices (GCP) guidelines and regulatory requirements and is considered appropriate for this study. Any changes to the proposed consent form suggested by the investigator must be agreed by Novartis before submission to the IRB/IEC.

Novartis will review the investigators/clinical research organization (CRO) proposed informed consent form to ensure it complies with the ICHE6 GCP guidelines and regulatory requirements and is considered appropriate for this study. Any further changes to the proposed consent form suggested by the investigator must be agreed to by Novartis before submission to the IRB/IEC.

Information about common side effects already known about the investigational drug can be found in the Investigator's Brochure (IB). This information will be included in the patient informed consent and should be discussed with the patient during the study as needed. Any new information regarding the safety profile of the investigational drug that is identified between IB updates will be communicated as appropriate, for example, via an investigator notification or an aggregate safety finding. New information might require an update to the informed consent and then must be discussed with the patient.

Women of child bearing potential must be informed that taking the study treatment may involve unknown risks to the fetus if pregnancy were to occur during the study and agree that in order to participate in the study they must adhere to the contraception requirements.

Male patients must be informed that if a female partner becomes pregnant while he is enrolled in the study, contact with the female partner will be attempted to request her consent to collect pregnancy outcome information.

[figure not shown]
A copy of the approved version of all consent forms must be provided to Novartis after IRB/IEC approval.

8 Visit schedule and assessments

Assessment schedule lists all of the assessments when they are performed. All data obtained from these assessments must be supported in the patient's source documentation.

Screening assessments can occur within 28 days prior to the enrollment as per [Table 8-1](#).

There is a \pm 1 day visit window permitted on assessments to take into account scheduling over public holidays, from Week 1 Day 1 to Week 9 Day 1. Also a visit window of \pm 3 days is allowed from Week 11 Day 1 to end of treatment.

A visit window of \pm 7 days is allowed during the follow-up period for responders.

Every effort should be made to follow the schedule outlined in [Table 8-1](#).

Patients should be seen for all visits/assessments as outlined in the assessment schedule or as close to the designated day/time as possible. Missed or rescheduled visits should not lead to automatic discontinuation. Patients who prematurely discontinue the study for any reason should be scheduled for a visit as soon as possible, at which time all of the assessments listed for the final visit will be performed. At this final visit, all dispensed eltrombopag study treatment supplies should be reconciled, and the adverse event and concomitant medications recorded on the CRF.

Table 8-1 Assessment schedule

Screening to Week 9

Period	Screening	Treatment									
		Week 1 Day 1	Week 2 Day 1	Week 3 Day 1	Week 4 Day 1	Week 5 Day 1	Week 6 Day 1	Week 7 Day 1	Week 8 Day 1	Week 9 Day 1	
Visit Name	Screening										
Visit Number	1	110	120	130	140	150	160	170	180	190	
IRT											
IRT registration	X										
IRT enrollment		X									

X = assessment to be recorded in the clinical database or received electronically from a vendor
S = assessment to be recorded in the source documentation only
a= Should be administered before IP administration
**= on monthly basis or as per local standard, if no visit planned the test can be performed at home with urine pregnancy test. Only blood test results will be collected in the eCRF)

Weeks 11 to follow-up

Period	Treatment																				End of Treatment	Safety Follow-up	
	Week 11 Day 1	Week 13 Day 1	Week 15 Day 1	Week 17 Day 1	Week 19 Day 1	Week 21 Day 1	Week 23 Day 1	Week 25 Day 1	Week 27 Day 1	Week 29 Day 1	Week 31 Day 1	Week 33 Day 1	Week 35 Day 1	Week 37 Day 1	Week 39 Day 1	Week 41 Day 1	Week 43 Day 1	Week 45 Day 1	Week 47 Day 1	Week 49 Day 1	Week 51 Day 1		
Visit Name	200	210	220	230	240	250	260	270	280	290	300	310	320	330	340	350	360	370	380	390	400	1999	SFUP
Visit Number																							
IRT enrollment																						X	

X = assessment to be recorded in the clinical database or received electronically from a vendor
S = assessment to be recorded in the source documentation only

* Patients who have achieved sustained remission at month 12 will be followed quarterly for an additional 12 months to obtain further data on response and remission duration.

** On monthly basis or as per local standard, if no visit planned the test can be performed at home with urine pregnancy. Only blood test results will be collected in the eCRF)

Follow-up Period for Responders

Period	Treatment				Safety Follow-up
Visit Name	FUP Visit #1 M15	FUP Visit #2 M18	FUP Visit #3 M21	End of FUP M24 ^b	Safety FUP
Visit Number	410	420	430	2999	SFUP
Physical Exam	S	S	S	S	
Height	S	S	S	S	
Weight	X	X	X	X	
Vital Signs	X	X	X	X	
Adverse Events	X				X
Prior/concomitant Medications	X				X
Pregnancy Test	S	S	S	S	
Laboratory Assessments					
Hematology	X	X	X	X	
Chemistry	X	X	X	X	
Patient Reported Outcomes					
FACIT-Fatigue	X	X	X	X	
FACT-Th6	X	X	X	X	
SF-36v2	X	X	X	X	
GP5				X	
TSQM-9				X	
Study Drug Administration ^a	X	X	X	X	

X = assessment to be recorded in the clinical database or received electronically from a vendor

S = assessment to be recorded in the source documentation only

a = If the patient relapses during the follow-up period, they may begin re-treatment with eltrombopag. If the patient is treated with treatment options other than eltrombopag they will discontinue the study at that time.

b = Patients who discontinue prior to month 24 and not at a defined study visit should come into complete the end of follow-up / month 24 visit.

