5.2 Exclusion criteria

Patients meeting **any** of the following criteria are not eligible for inclusion in this study.

1. ITP patients previously treated with any ITP second-line therapies, TPO-RA for ITP, except steroids / IVIG as described in the inclusion criteria
2. Patients who relapsed more than one year after the end of first-line full course of steroid therapy
3. Patients with a diagnosis of secondary thrombocytopenia.
4. Patients who are unable to participate in assessments/biological studies
5. Patients who have life threatening bleeding complications per investigator discretion
6. Patients who had a deep vein thrombosis or arterial thrombosis in the 6 months preceding enrollment
7. Presence of moderate to severe impaired renal function as indicated by any or all of the following criteria:
 - Creatinine clearance $< 45 \text{ mL/min}$ as calculated using Cockcroft-Gault formula
 - Serum creatinine $> 1.5 \text{ mg/dL}$
8. Total bilirubin $> 1.5 \times$ upper limit of normal (ULN)
9. Aspartate transaminase (AST) $> 3.0 \times$ ULN
10. Alanine transaminase (ALT) $> 3.0 \times$ ULN
11. Patients who are human immune deficiency virus (HIV), hepatitis C virus (HCV) or hepatitis B surface antigen (HBsAg) positive. These assessments can be performed using the local laboratory used by the site. Central laboratory testing is available for HIV, HCV, and HBsAg should local laboratory testing not be available.
12. Patients with hepatic impairment (Child-Pugh score > 5)
13. Patients who are unable to respect the 4-hour interval between eltrombopag and other medications (e.g., antacids), calcium-rich foods (e.g., dairy products and calcium fortified juices), or supplements containing polyvalent cations such as iron, calcium, aluminum, magnesium, selenium, and zinc
14. Patients who are unable to stop medications that are known to cause a drug-drug interaction with eltrombopag
15. Patients who have active malignancy
16. Patients with any serious and/or unstable pre-existing medical, psychiatric disorder or other conditions that could interfere with patient's safety, obtaining informed consent or compliance with the study procedures as per investigator discretion
17. Patients with a known immediate or delayed hypersensitivity reaction or idiosyncrasy to eltrombopag or drugs chemically related to eltrombopag or excipients that contraindicate their participation

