6.2.1.1 Permitted concomitant therapy requiring caution and/or action

HMG-CoA Reductase Inhibitors (statins)

Patients will be permitted to use HMG-CoA reductase (3-hydroxy-3-methyl-glutaryl-CoA) inhibitors during the study, but these drugs should be used with caution and a 50% dose reduction of the HMG-CoA reductase inhibitor is recommended, with close monitoring for safety, such as liver chemistry and signs and symptoms of myolysis, and efficacy, such as cholesterol and triglycerides (refer to individual product information for monitoring recommendations).

Polyvalent Cations (Chelation)

Eltrombopag chelates with polyvalent cations such as aluminum, calcium, iron, magnesium, selenium and zinc. Eltrombopag should be taken at least two hours before or four hours after

any products such as antacids, dairy products, or mineral supplements containing polyvalent cations to avoid significant reduction in eltrombopag absorption.

Food Interaction

To avoid significant reduction in eltrombopag absorption, eltrombopag should be taken at least two hours before or four hours after food containing > 50 mg calcium and at least one hour before to two hours after food containing little (< 50 mg) (or preferably no) calcium. The administration of a single 50 mg dose of eltrombopag with a standard high-calorie, high-fat breakfast that included dairy products led to reduced eltrombopag exposure. Foods low in calcium (defined as < 50 mg calcium per serving) including fruit, lean ham, beef and unfortified (no added calcium, magnesium, iron) fruit juice, unfortified soy milk, and unfortified grain did not significantly impact plasma eltrombopag exposure, regardless of calorie and fat content.

Substrates of OATP1B1 or BCRP

Concomitant administration of eltrombopag and other OATP1B1 or BCRP substrates should be undertaken with caution.

Examples of drugs which are OATP1B1 or BCRP substrates are given in [Appendix 16.1](#).

CYP and UGT inhibitors and inducers

Eltrombopag is metabolised through multiple pathways including CYP1A2, CYP2C8, UGT1A1, and UGT1A3. Medicinal products that inhibit or induce a single enzyme are unlikely to significantly affect plasma eltrombopag concentrations; whereas medicinal products that inhibit or induce multiple enzymes have the potential to increase (e.g. fluvoxamine) or decrease (e.g. rifampicin) eltrombopag concentrations.

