6.7 Preparation and dispensation

The investigator or responsible site personnel must instruct the patient or caregiver to take the study drugs as per protocol. Eltrombopag will be dispensed to the patient by authorized site personnel only. All dosages prescribed to the patient and all dose changes during the study must be recorded on the Dosage Administration Record eCRF.

[figure not shown]

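### The dosing instruction in Protocol 6.7.2 swaps the calcium-spacing hours of 6.2.1.1 and so permits calcium-rich food 2 to 4 hours before a dose

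*Protocol*

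**What the plan says.** Protocol 6.2.1.1 gives the spacing rule twice. Under the polyvalent-cation heading it reads "Eltrombopag should be taken at least two hours before or four hours after", and the sentence goes on to cover "any products such as antacids, dairy products, or mineral supplements containing polyvalent cations to avoid significant reduction in eltrombopag absorption". Under the food heading it reads "eltrombopag should be taken at least two hours before or four hours after food containing > 50 mg calcium". For food with little calcium (under 50 mg) the same section is more lenient: the dose may be taken from one hour before to two hours after.

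Protocol 6.7.2, the section on how patients take the drug, has two relevant bullets. The general meal bullet reads "Patients should take eltrombopag at approximately the same time each day either 1 hour before eating or 2 hours after eating". The calcium bullet begins "For 2 hours before taking eltrombopag and 4 hours after taking eltrombopag, patients should" and then names dairy and foods rich in calcium or magnesium as the things to avoid.

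Two other places bear on the point. Protocol 6.7 says that site staff "must instruct the patient or caregiver to take the study drugs as per protocol". Exclusion criterion 13 in Protocol 5.2 removes "Patients who are unable to respect the 4-hour interval between eltrombopag and other medications", and its list continues to calcium-rich foods and cation supplements.

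**The concern.** The two sections measure from opposite ends. Section 6.2.1.1 places the dose relative to the food; 6.7.2 places the food relative to the dose. Two hours before the food and four hours after it, restated from the dose, becomes four hours clear before the dose and two hours clear after it. Section 6.7.2 kept the order of the numbers while changing the reference point, which reversed the rule.

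The reversal opens the gap before the dose, where 6.2.1.1 asks for the longer interval. Eltrombopag is the only study treatment, and 6.2.1.1 says the spacing exists to prevent a significant drop in its absorption. If calcium taken 2 to 4 hours earlier does reduce absorption, a patient who follows 6.7.2 faithfully could be under-exposed. Table 6-3 raises the dose when platelets stay below 100×10⁹/L after two weeks, so low absorption could be mistaken for inadequate response. Section 6.5.2.1 also requires permanent discontinuation for significant non-compliance, yet the same day's dosing can satisfy 6.7.2 and breach 6.2.1.1.

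**Working it through.** No sample-size or power figure is involved. The check puts both rules on one clock, with the dose at E.

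**Converting 6.2.1.1.** A dose at least 2 h before food means food no earlier than E+2 h. A dose at least 4 h after food means food no later than E−4 h. Calcium is therefore barred between E−4 h and E+2 h, a window of 4 + 2 = 6 h. Both statements in the section give this window.

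**Reading 6.7.2.** The calcium bullet is already stated from the dose: barred between E−2 h and E+4 h, a window of 2 + 4 = 6 h.

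**Comparing them.**

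| Interval around dose E | 6.2.1.1 | 6.7.2 calcium bullet | Consequence |
|---|---|---|---|
| E−4 h to E−2 h | barred | allowed | gap of 2 h |
| E−2 h to E+2 h | barred | barred | agree |
| E+2 h to E+4 h | allowed | barred | 6.7.2 stricter |

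The gap is 2 of the 6 barred hours (2/6 = 33%). This is a share of clock time; it is not a share of doses, patients or exposure.

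**Does the general meal bullet close the gap?** It permits dosing 2 h after eating, with no calcium limit. The calcium bullet also asks for 2 h before the dose. On the pre-dose side it therefore adds 2 − 2 = 0 h to what any meal already requires. Section 6.2.1.1 allows the 2 h interval only after low-calcium food.

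**Worked example.** Dairy breakfast at 07:00, dose at 09:30, gap 2.5 h. Under 6.7.2 the requirement is 2 h, so both bullets are met. Under 6.2.1.1 the requirement is 4 h, so the dose is 4 − 2.5 = 1.5 h too early; the earliest permitted time is 11:00.

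**Is the difference a recorded change?** The Amendment 1 list mentions 6.2.1.1 only for added text on CYP and UGT inhibitors and inducers, and does not list 6.7.2. Both sections are current text.

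**After correction.** With 4 h before and 2 h after in 6.7.2, the barred window is E−4 h to E+2 h, identical to 6.2.1.1, and 0 h is left open. A rule of 4 h on both sides also leaves 0 h open, with a window of 4 + 4 = 8 h.

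**The case against.** The strongest counter-argument is that the two sections can both be obeyed. A site that applies them together keeps calcium out from E−4 h to E+4 h. Exclusion 13 supports that reading, since an interval of four hours with no direction is most naturally four hours on either side. On the pre-dose side, then, three statements point to four hours and one bullet to two, and an instruction to follow the protocol includes 6.2.1.1. This narrows the problem: it arises only where a site or patient works from 6.7.2 alone. It does not remove it. Section 6.7.2 is the section headed as the instruction for taking the drug, it does not refer back to 6.2.1.1, and nothing tells a site to combine the two. Exclusion 13 tests at enrolment whether a patient can comply; it is not the dosing rule.

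It is also fair that no clinical effect is shown. The one exposure result in 6.2.1.1 concerns a dose taken together with a breakfast that included dairy, not one taken 2 to 4 hours later. Platelets are checked weekly for the first eight weeks and every two weeks after that, and the dose is titrated to them, so part of any loss would be offset, except in patients already at the 75 mg cap. These points stand and limit the weight of the finding.

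Finally, the silence of 6.7.2 on antacids and supplements, and the lack of a calcium limit in its meal bullet, are not separate errors. Section 6.2.1.1 covers both.

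**Conclusion.** The inconsistency is real and should be fixed. Section 6.7.2 reverses the spacing that 6.2.1.1 states twice, and leaves open the two hours from E−4 h to E−2 h. It is most likely a transposition, since the protocol gives no reason for a second rule.

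The size of any effect on exposure or response cannot be computed: the documents give neither the absorption loss at a 2 to 4 hour gap nor how often patients would eat calcium-rich food in that band. Any uncorrected loss would tend to reduce the observed remission rate, so it would not produce a false positive. The sample size, the null proportion and the binomial test do not change.

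The conclusion takes 6.2.1.1 as the intended rule, because it is stated twice there with its reason. The SAP reports that all 105 patients are already enrolled, and the documents do not show what patients were actually told, so the finding concerns the plan as written.

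**What to change.** Change the calcium bullet in Protocol 6.7.2 to 4 hours before and 2 hours after taking eltrombopag. If the sponsor prefers one rule that is easy to remember, 4 hours on both sides also works and agrees with the natural reading of exclusion 13. Use the same wording wherever sites instruct patients.

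Three further edits are optional: extend the bullet to antacids and mineral supplements, limit the allowance of two hours after eating to low-calcium food, and have exclusion 13 refer to the corrected rule.

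The required change is one bullet plus matching patient instructions. It adds no visits, procedures or patients, and leaves the analysis as it is.

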8.1 Screening

All patients will be screened for study eligibility. All patients must sign informed consent prior to any screening procedures being performed. Activities for screening will begin up to 28 days prior to initiation of study treatment with eltrombopag.

Information regarding eligibility criteria will be collected on the Inclusion/Exclusion eCRF. Patients who do not meet all entry criteria should not be entered into the study.

A re-screening due to lab abnormalities can be submitted to the sponsor for decision. Re-screening of patients is only allowed **once** per patient if the patient was not enrolled in the treatment phase before. If patient has been enrolled and treated, re-screening of patient is not allowed.

In case rescreening occurs, all evaluations to be re-assessed should meet the eligibility criteria. A new informed consent form must be signed only if there is an interruption in the patient's eligibility evaluation and the investigator chooses to re-screen the patient following screen failure; the 28 day screen period does not apply to the informed consent process. If a new informed consent form is signed, AEs and medical history will be assessed relative to the new informed consent date.

Following registering in the Interactive Response Technology (IRT) for screening, patient eligibility will be checked once all screening procedures are completed. The eligibility check will be embedded in the IRT system. Please refer and comply with detailed guidelines in the IRT manual.

8.1.1 Information to be collected on screening failures

Patients who sign an informed consent form and subsequently found not to be eligible will be considered a screen failure. The reason for screen failure should be entered on the applicable CRF. The demographic information, informed consent, and Inclusion/Exclusion pages must also be completed for screen failure patients. No other data will be entered into the clinical database for patients who are screen failures, unless the patient experienced an SAE event during the screening phase (see [Section 10.1.3](#) for reporting details).

Patients who sign an ICF and are considered eligible but fail to be started on treatment for any reason will be considered an early terminator. The reason for early termination should be captured on the appropriate disposition CRF.

8.2 Patient demographics/other baseline characteristics

Country specific regulations should be considered for the collection of demographic and baseline characteristics in alignment with CRF

The following patient demographics and baseline characteristics will be collected on the eCRF:

- Demography including age, sex, predominant race and ethnicity (where permitted)
- Height and weight
- Medical history (e.g., important medical, surgical, and allergic conditions from the patient's medical history which could have an impact on the patient's evaluation)/ current medical conditions (e.g., all relevant current medical conditions which are present at the time of signing informed consent). Ongoing medical conditions, symptoms and diseases which are recorded on the Medical History eCRF should include the toxicity grade when applicable
- Prior and concomitant medications

Bone marrow biopsy is optional and recommended for patients who did not respond to steroids and are considered refractory. It can be performed during treatment at the discretion of the investigator.

All assessments to be completed and documented during screening are detailed in [Table 8-1](#).

